4.2.17.3 Handling of Dropouts and Missing Data

Missing PAINS-pNF data after treatment discontinuation is handled by the “while on-treatment” approach, using the PAINS-pNF of cycles where a patient was on treatment.

4.2.17.4 Primary Analysis of PAINS-pNF Spike Target PN Pain Intensity

The primary analysis for PAINS-pNF spike target PN pain intensity score will mirror the primary analysis of the 2nd key secondary endpoint, as described in Section [4.2.2.5](#), that is, the maximum score during the randomised period will be compared between arms using an MMRM model with treatment and geographical region as factors as well as baseline spike pain intensity score as a covariate and baseline spike pain intensity score-by-cycle and treatment-by-cycle as interactions. The LS mean (95% CI) in each study intervention arm as well as the treatment difference and p-value will be presented at each cycle and

overall, in the randomised period. A plot of the LS means accompanied by the 95% CI will be produced.

The analysis will be performed on the FAS population with a baseline score and at least one post-baseline assessment for spike target PN pain intensity.

4.2.17.5 Additional Analyses of PAINS-pNF Spike Target PN Pain Intensity

PAINS-pNF spike target PN pain intensity actual scores and change from baseline will be summarised descriptively by study intervention arm. If there are instances of early crossover, then some cycles prior to Cycle 12 will summarise data of placebo subjects who have already crossed over to selumetinib. Summary statistics will include n, mean, standard deviation, min, Q1, median, Q3, and max. Plots of the mean scores, as well as the changes from baseline and the associated 95% CIs by cycle will be produced for the randomised period.

The analysis will be performed on the FAS.

4.2.18 Percentage Change From Baseline in Target PN Volume in the Fed State

4.2.18.1 Definition

See Section [4.2.1.2](#).

4.2.18.2 Derivations

Since the date of switching to the fed state from Cycle 25 Day 1 is not at a fixed timepoint, the time from the fed state will be derived cycles which will be re-numbered in relation to the switch point. Any cycle after the switch will be re-labelled as “Fed Cycle 1” (i.e., the first cycle after the switch), “Fed Cycle 2” (i.e., the second cycle after the switch), etc. Any cycle prior to the switch will be re-labelled as “Fed Cycle -1” (i.e., the last cycle before the switch), “Fed Cycle 2” (i.e., the second-to-last cycle before switch), etc.

The date of switching to the fed state (see Section [3.2.10](#) for the definition of the fed state) will be the maximum date between Cycle 25 Day 1 (based on the drug accountability form) and the day after the ICF signature for the CSP v4.0.

In an ideal situation when the patient switch date to the fed state corresponds to Cycle 25 Day1, the following map yields:

	Time from randomisation (timepoint)	Time from the fed state (timepoint)
	Baseline	Baseline
Fasting state	Cycle 1 Day 28	Fed Cycle -24
	Cycle 8 Day 28	Fed Cycle -16

	Cycle 12 Day 28	Fed Cycle -12
	Cycle 16 Day 28	Fed Cycle -8
	Cycle 20 Day 28	Fed Cycle -4
	Cycle 24 Day 28	Fed Cycle -1
Fed state	Cycle 30 Day 28	Fed Cycle 6
	Cycle 36 Day 28	Fed Cycle 12

4.2.18.3 Handling of Dropouts and Missing Data

Analyses will be based on available data.

4.2.18.4 Primary Analysis

The percentage change from baseline in target PN volume over time from the fed state switch will be presented using box plots and summary statistics in the Fed FAS. The individual percentage change from baseline over time from the fed state switch will also be shown in a line plot. For patients randomised to placebo, these will include data prior and post selumetinib intervention initiation.

The time from the fed state will be listed together with the time from randomisation in the listing of target PN visit response.

4.2.19 PGIS and PGIC

4.2.19.1 Definition

The PGIS is a self-reported one-item instrument that evaluates target PN symptom severity (with separate single items for chronic pain and spike pain) over the past 7 days on a 4-point scale (1 = No pain, 2 = Mild, 3 = Moderate, and 4 = Severe).

The PGIC is a self-reported two-item instrument that evaluates the patient's perspective of changes in their PN-related pain (with separate two items for chronic pain and spike pain) on a 7-point scale (from 1 = Much better to 7 = Much worse) since their last visit to the study site and since starting the study medication.

The PGIS and the PGIC are planned to be collected at the end of Cycles 1, 2, 4, 6, 8, 10, and 12. The PGIS is also collected at baseline.

4.2.19.2 Analysis of PGIS and PGIC

Descriptive statistics (counts and percentages) of the item score for each question (chronic pain and spike pain) will be produced by treatment and visit for PGIS and PGIC (one table for each PRO).

A shift table will also be provided for the PGIS, showing the distribution of the responses by treatment at the end of Cycle 12 by baseline PGIS response.

The analyses will be performed on the FAS population.

4.3 Pharmacodynamic Endpoint(s)

See Section 4.4.

4.4 Pharmacokinetics

This section covers the non-compartmental PK endpoints and analyses.

Details of population PK exposure response/safety analyses will be described in the modelling analysis plan that will be finalised before database lock. The population PK exposure response/safety analyses will be presented separately from the main CSR.

4.4.1 Calculation or Derivation of PK Parameters

The PK parameters for selumetinib and N-desmethyl selumetinib will be derived using non-compartmental methods in Phoenix® WinNonlin® Version 8.1 or higher (Certara).

The PK parameters will be derived according to AstraZeneca PK standards.

PK analysis will, where data allow, be carried out using actual elapsed times determined from the PK sampling and dosing times recorded in the database. If actual elapsed times are missing, nominal times may be used.

Where data allow, the following PK parameters for selumetinib and N-desmethyl selumetinib will be derived from Cycle 1 Day 8 plasma concentrations.

PK Parameters

Cmax	Maximum observed concentration
tmax	Time to reach maximum observed concentration following drug administration
AUC(0-6)	Partial area under the concentration-time curve from time 0 to 6 hours
AUC(0-8)	Partial area under the concentration-time curve from time 0 to 8 hours
AUClast	Area under the concentration-curve from time 0 to the last quantifiable concentration
CL/F	Apparent total body clearance of drug from plasma after extravascular administration (selumetinib only)
Vss/F	Volume of distribution (apparent) at steady state following extravascular administration (selumetinib only)
MPAUC	Metabolite: parent ratio based on AUC ^a
MPCmax	Metabolite: parent ratio based on Cmax
tlast	Time of last observed concentration

^a Will be based on either AUC(0-6) or AUC(0-8) depending on which has the most reportable values.

Additional PK parameters may be determined where appropriate.

If an entire concentration-time profile is not quantifiable, the profile will be excluded from the PK analysis.

The minimum requirement for the calculation of area under the concentration-time curve values will be the inclusion of at least 3 consecutive quantifiable concentrations. Where there are only 3 quantifiable concentrations at least one of these should follow the peak concentration.

4.4.2 Presentation of PK Data

The plasma selumetinib and N-desmethyl selumetinib concentrations and the PK parameters will be listed and presented in tabular and graphical form as appropriate according to the version of the AstraZeneca Corporate CSRHLD TFL templates and reporting standards as documented in the TFL shells, that includes applicable descriptive statistics, defined handling of individual concentrations below the Lower Limit of Quantification (LLOQ), and precision/rounding rules for concentrations and PK parameter data.

Exclusion of concentration and/or parameter data from PK summaries may apply, this will be flagged in the listings with the reason(s) for exclusion.

PK sampling is targeted for Day 8, however for operational reasons the PK sampling can take place on any day between Day 4 and Day 14 as long as the patient has received 3 consecutive days of dosing immediately prior to the PK Day. Every effort should be made to conduct PK sampling within the Day 4 - Day 14 window. However, if for unforeseen reasons this is not possible, PK sampling can be performed at any time within the first cycle provided the patient has received 3 consecutive days of dosing immediately prior to the PK day and all data will be reported and summarised as multiple dose PK data.

4.4.2.1 Plasma Concentrations

Selumetinib and N-desmethyl selumetinib plasma concentrations for each scheduled timepoint will be listed and summarised by analyte based on the PK Analysis Set. A listing of all concentration-time data, i.e., PK scheduled times, actual sample collection times, sample actual relative times, as well as derived sampling time deviations will be presented based on the Selumetinib FAS.

4.4.2.2 PK Parameters

Individual PK parameters for selumetinib and N-desmethyl selumetinib PK parameters will be listed and summarised by analyte, based on the PK Analysis Set.

4.4.2.3 Graphical Presentation

Individual concentration-time data will be graphically presented on linear and semi-logarithmic scales, for the PK Analysis Set. Each individual's plot will include the

concentration versus actual time profiles for both analytes overlaid on the same plot. Combined individual plasma concentration versus actual times grouped by treatment will be plotted separately by analyte, on both the linear and semi-logarithmic scale in the PK Analysis Set.

Figures of geometric mean concentrations versus schedule time will be presented separately by analyte, on both a linear scale with geometric Standard Deviation (gSD) error bars and semi-logarithmic scale (no error bars), based on the PK Analysis Set.

4.5 Immunogenicity

Not applicable.

4.6 Safety Analyses

The domain safety covers exposure, AEs, clinical laboratory, vital signs, electrocardiogram (ECG), ophthalmological assessments, physical examination, and Eastern Cooperative Oncology Group (ECOG) performance score.

Tables are provided for both the randomised period safety analysis set and the on-selumetinib safety analysis set. Listings are provided for the safety analysis set only.

4.6.1 Exposure

4.6.1.1 Definitions and Derivations

Exposure will be defined as follows:

- Total (or intended) exposure = min (last dose date of selumetinib/placebo where dose > 0 mg, date of death, DCO Date) – first dose date of selumetinib/placebo + 1
- Actual exposure = Total (or intended) exposure – total duration of dose interruptions, where total (or intended) exposure will be calculated as above. A dose interruption is defined as either any day with dose = 0 mg, or any half day where planned frequency is bid but actual frequency is daily, during the treatment period.

This calculation will use the individual start and stop dates on the EX form of the CRF, which will account for any dose interruptions. The actual exposure calculation makes no adjustment for any dose reductions that may have occurred.

Exposure will also be measured by the number of cycles received. A cycle corresponds to a period of 28 days. A cycle will be counted if study intervention is started even if the full dose is not delivered.

Exposure will be derived for selumetinib and placebo. Patients who only received selumetinib will only have exposure records for selumetinib, while patients who received placebo and selumetinib will have exposure records for selumetinib and placebo.

Patients Who Permanently Discontinue During a Dose Interruption

If a patient permanently discontinues study intervention during a dose interruption, then the date of last administration of study medication will be used in the calculation of exposure. In this case, the interruption would not be included in the summary tables, but it will be included in the listings.

Relative Dose Intensity

Relative dose intensity (RDI) is the percentage of the actual dose delivered relative to the intended dose through to study intervention discontinuation. RDI will be defined as follows:

RDI = $100\% * \frac{d}{D}$, where d is the actual cumulative dose delivered up to the actual last day of dosing and D is the intended cumulative dose up to the day of treatment discontinuation or the actual last day of dosing. D is the total dose that would be delivered if the patient received the planned dose as per the CRF. Intended cumulative dose will be calculated by summing the individual doses that should have been received up to and including the last day of treatment according to the protocol planned dose and schedule. This is given by:

Integer part (rounded up) of $((\min(\text{date of last dose date where dose} > 0, \text{date of death, date of DCO}) - \text{first dose date} + 1) \times \text{intended dose according to the protocol})/0.5$.

The intended dose for Selumetinib is $25 \text{ mg/m}^2 \text{ bid}$.

The actual cumulative dose will be calculated by summing $((\text{End date of study drug administration} - \text{Start date of study drug administration} + 1) \times \text{Dose})/0.5$ for each period of study drug administration recorded on the study drug exposure form up to $\min(\text{date of last dose where dose} > 0, \text{date of death, date of DCO})$.

Compliance

Percentage compliance is the percentage of the actual cumulative dose delivered relative to the cumulative dose the patient should have received according to the protocol including protocol allowable dose reductions/dose interruptions up to and including the last day of day of treatment.

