**Table 6      Body Surface Area Dosing Guidelines**

Body surface area (m  )	Selumetinib starting dose (mg) a	
	AM	PM
1.1 to 1.29	30	30
1.3 to 1.49	35	35
1.5 to 1.69	40	40
1.7 to 1.89	45	45
≥ 1.90	50	50

a Actual dose in mg (capsule sizes 10 and 25 mg) administered every 12 hours to achieve a dosage of 25 mg/m^2 bid. bid, twice daily.

Study intervention capsules should be swallowed whole with a glassful of water twice a day, approximately 12 hours apart but no less than 6 hours apart, on an empty stomach (no food or drink other than water for 2 hours prior to dosing and one hour after dosing).

From the end of Cycle 24 (Cycle 25 Day 1) participants will not be required to continue to observe the fasting restriction described above, meaning that the participant can eat at any time point in relation with each selumetinib intake. Participants will be therefore considered in fed state. Refer to [Section 5.2.1](#) for the definition of participant fed state.

If a dose of study treatment is missed, it should only be taken if it is more than 6 hours until the next scheduled dose. If vomiting occurs after study treatment administration, an additional dose should not be taken. Dosing should be continued with the next scheduled dose.

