### **Selumetinib**

Participants in the selumetinib group will receive 25 mg/m^2 selumetinib as oral capsules bid. Dosing will be based on BSA and capped at 50 mg bid when BSA is ≥ 1.9 m^2.

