It is estimated that approximately 212 adult patients will be enrolled at approximately 46 sites across 13 countries to achieve approximately 146 patients randomised to study intervention. Patients will be randomised 1:1 to receive selumetinib or placebo (i.e. 73 patients per arm). Randomisation will be stratified at the central level by average baseline PAin INTensity Scale for Plexiform Neurofibroma (PAINS-pNF) chronic target PN pain score (< 3 and \geq 3) and geographical region (Europe, China, Japan, and Rest of World). A blocked randomisation will be generated, and randomisation will be balanced within the IRT at the central level. The number of patients randomised will be capped at approximately 106 patients with an average baseline PAINS-pNF chronic target PN pain score \geq 3 and approximately 40 patients with an average baseline PAINS-pNF chronic target PN pain score < 3. Patients randomised to selumetinib will receive selumetinib 25 mg/m² orally twice daily (bid) (based on body surface area [BSA], capped at 50 mg bid when BSA is \geq 1.9 m²) in 28-day cycles until a selumetinib discontinuation criterion is met. Patients randomised to placebo will receive placebo orally bid and will receive selumetinib treatment after the end of Cycle 12. Selumetinib capsules will be administered using BSA-based dosing. If it is anticipated that 20% or more of patients (across blinded study intervention groups) withdraw prior to the end of Cycle 16 for reasons other than progression, then recruitment rates notwithstanding, enrolment will continue to randomise at least 50% of the total number of dropout patients to ensure that the primary endpoint is adequately powered.

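### SAP 4.6.1.1 describes the RDI denominator in two ways that do not agree as written: the planned dose in the CRF, and 25 mg/m² bid with no BSA bands, cap or conversion to mg

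*SAP*

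**What the plan says.** SAP 4.6.1.1 says that RDI "is the percentage of the actual dose delivered relative to the intended dose through to study intervention discontinuation", computed as 100% × d/D, where d is the actual and D the intended cumulative dose.

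D is then described three times:

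- "D is the total dose that would be delivered if the patient received the planned dose as per the CRF".
- As the sum of the doses due "according to the protocol planned dose and schedule".
- As a formula: days on treatment times "intended dose according to the protocol", divided by 0.5 and rounded up. The next sentence supplies the input: "The intended dose for Selumetinib is" 25 mg/m² bid.

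Protocol 6.1.1 sets the dose in mg. Table 6 gives 30, 35, 40, 45 or 50 mg twice daily by BSA band. Its footnote describes these as "Actual dose in mg (capsule sizes 10 and 25 mg) administered every 12 hours to achieve a dosage of 25 mg/m"² bid. The Selumetinib paragraph adds: "Dosing will be based on BSA and capped at 50 mg bid when BSA is" at least 1.9 m². The SAP repeats the cap in its design summary, section 1.1 ("capped at 50 mg bid when BSA is" at least 1.9 m²), but not in 4.6.1.1.

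SAP 4.6.1.2 summarises RDI by treatment group and treatment, for the randomised period and the on-selumetinib period.

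**The concern.** The first two descriptions point to a planned dose in mg. The last gives a dose per square metre and stops there. A programmer who works from the formula and the sentence below it needs D in mg to match d, and the obvious step is to multiply 25 by the participant's BSA. A programmer who works from the first description would take the planned mg dose. The same data then give different RDIs.

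RDI is meant to show how much planned dose was lost to interruptions and reductions. With 25 × BSA underneath, it also measures body size. A large participant with perfect dosing looks under-dosed, and one at the bottom of a band shows more than 100% without any extra dose.

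**Working it through.** **Inputs.** Band limits and doses: protocol Table 6. Cap of 50 mg bid: protocol 6.1.1 and SAP 1.1. Literal intended dose of 25 mg/m² bid: SAP 4.6.1.1. The documents state no RDI value to reproduce, so the check starts from Table 6.

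**Step 1: reproduce Table 6.** Taking 25 × BSA, rounding to the nearest 5 mg (halves up) and capping at 50 mg returns the tabulated dose at every 0.01 m² of the four closed bands, and 50 mg from 1.90 m². For example, 25 × 1.10 = 27.5 and 25 × 1.29 = 32.25 both round to 30. The cap changes the rounded dose from 2.1 m², where 25 × 2.1 = 52.5 would round to 55. Table 6 is therefore the rounded and capped form of 25 mg/m².

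**Step 2: RDI with full dosing, literal reading.** Days and the division by 0.5 appear in both d and D and cancel, and rounding D up is negligible (checked over 336 days). So

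RDI = 100 × Table 6 dose / (25 × BSA).

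| BSA (m²) | Dose (mg bid) | RDI, bottom of band | RDI, top of band |
|---|---|---|---|
| 1.10–1.29 | 30 | 30/27.5 = 109.1% | 30/32.25 = 93.0% |
| 1.30–1.49 | 35 | 35/32.5 = 107.7% | 35/37.25 = 94.0% |
| 1.50–1.69 | 40 | 40/37.5 = 106.7% | 40/42.25 = 94.7% |
| 1.70–1.89 | 45 | 45/42.5 = 105.9% | 45/47.25 = 95.2% |

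The top band is open-ended. At its lower limit, 1.90 m², RDI is 50/47.5 = 105.3%. It reaches 50/50 = 100% at 2.0 m² and keeps falling. The documents give no upper BSA, so the following values are assumptions: 2.2 m², 50/55 = 90.9%; 2.5 m², 50/62.5 = 80.0%; 2.8 m², 50/70 = 71.4%.

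**Step 3: RDI with full dosing, planned mg dose.** Numerator and denominator are the same banded, capped dose, so RDI = 100% at every BSA.

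**Step 4: what the literal reading does to interpretation.** At BSA 1.10 m², the first reduction in protocol Table 7 is 25 mg AM and 20 mg PM. Over days on that dose, the literal RDI is 45/(2 × 27.5) = 45/55 = 81.8%. A participant with no reduction at an assumed BSA of 2.4 m² has 50/60 = 83.3%. The two look alike. With the planned mg dose they are 45/60 = 75% and 100%.

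**The case against.** The best defence is that the protocol uses 25 mg/m² bid as the name of the banded, capped regimen. Table 5 gives that dosage level and sends the reader to the BSA table. The Table 6 footnote presents the mg doses as the way the dosage is achieved. The first description of D in SAP 4.6.1.1 already names the planned dose in the CRF. The formula contains no multiplication by BSA; taken at its word it is not in mg at all, which suggests a label rather than a programming input. On this view there is one denominator, the Table 6 dose, and RDI is 100% under full dosing.

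Much of this stands. A reader might infer that the SAP has chosen an unbanded, uncapped denominator. The documents do not support that: the sentence omits the bands and the cap, but nothing excludes them. A reader might also take a single low figure, such as 77% (50/65, at 2.6 m²), as what large participants would show. That is not supported either, because no BSA distribution or maximum is given.

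What does not stand is that nothing needs changing. The sentence beneath the formula is its only stated dose input, it needs a conversion that the SAP does not supply, and the obvious conversion gives a different answer from the definition above it.

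**Conclusion.** SAP 4.6.1.1 is internally inconsistent as written, and a reading that harmonises it is available. If programmed as 25 × BSA, fully dosed participants would show RDI of 93.0% to 109.1% in the closed bands, which follows from Table 6 alone. Above 2.0 m² they would fall below 100% by an amount that depends on BSAs the documents do not give. With the planned mg dose, RDI is 100% throughout. All these figures assume that every planned dose is taken and that BSA stays constant.

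The consequence is limited. No stated figure in the SAP is miscalculated. RDI enters no hypothesis test, and interruptions, reductions and compliance are summarised separately. The point concerns only the denominator of a descriptive measure and says nothing about which dose is right.

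**What to change.** Replace the sentence that gives the intended dose as 25 mg/m² bid with wording such as: *For D, the intended dose is the participant's protocol-planned dose in mg for their BSA (protocol Table 6, banded and capped), updated when BSA changes, before any toxicity-related reduction.* This brings the formula into line with the definition above it, protocol 6.1.1 and SAP 1.1.

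The last clause matters. Pointing only to the planned dose in the CRF could be read as the current dose after a reduction. A dose-reduced participant would then show 100%, and RDI would overlap with the compliance measure in the same section, which already allows for reductions and interruptions that the protocol permits. The sentence should also say whether a dose lowered for a co-administered CYP inhibitor (protocol Appendix J) counts for D as planned or as reduced.

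The cost is one SAP sentence and the matching line in the programming specification. No new data are needed, since weight and BSA are already scheduled in protocol Table 1 and doses are recorded on the exposure form.

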**Table 7 Dose Modification Procedure**

Body surface area (m^2)	Selumetinib starting dose (mg) a		First selumetinib dose (mg) reduction		Second selumetinib dose (mg) reduction	
	AM	PM	AM	PM	AM	PM
1.1. to 1.29	30	30	25	20	20	10
1.3 to 1.49	35	35	25	25	25	10
1.5 to 1.69	40	40	30	30	25	20
1.7 to 1.89	45	45	35	30	25	20
≥ 1.90	50	50	35	35	25	25

a Actual dose in mg (capsule sizes 10 and 25 mg) administered every 12 hours to achieve a dosage of 25 mg/m^2 bid, twice daily.

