**Table J15 Recommended Dosage of Selumetinib for Co-administration with Strong or Moderate CYP2C19 or CYP3A4 Inhibitors**

BSA (m  )	If the current dosage is up to 25 mg/m  bid, reduce to 20 mg/m  bid		If the current dosage is up to 20 mg/m  bid, reduce to 15 mg/m  bid	
	AM	PM	AM	PM
1.10 – 1.29	25	25	25	10
1.30 – 1.49	30	25	25	20
1.50 – 1.69	35	30	25	25
1.70 – 1.89	35	35	30	25
≥ 1.90	40	40	30	30

bid, twice daily; BSA, body surface area; CYP, cytochrome P450.

Changes to, or addition of medications detailed in [Table J16](#) and [Table J17](#) should be avoided, unless clinically indicated. The lists in [Table J16](#) and [Table J17](#) are not intended to be exhaustive, and a similar restriction will apply to other agents that are known to affect CYP2C19, or CYP3A4 activity. Appropriate medical judgment is required. Please contact AstraZeneca with any queries.

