4.6.1.2 Presentation

Total (or intended) exposure, actual exposure, number of cycles received, RDI, and number of dose interruptions, dose reductions, and dose modifications (either a dose interruption or

a dose reduction) will be summarised for each treatment group and treatment. Exposure will be summarised for the randomised period and on-selumetinib safety analysis set. For the randomised period safety analysis set, the exposure will be separated by placebo and selumetinib. For the on-selumetinib safety analysis set, the exposure will be separated by treatment arm and will include an overall summary.

Exposure data will be listed. Date of first exposure to treatment, total exposure (days), actual exposure (days), number of cycles received, RDI and compliance to IP will be summarised at period-level for the randomised period and on-selumetinib period. Additionally, details on all dose interruptions and reductions will be summarised including, reason for action taken, start and end date of interruption/reduction and dose per administration.

Percentage treatment compliance summarised as a continuous variable and counts using categories: eg, 100%, $\geq 95\% - < 100\%$, $\geq 90\% - < 95\%$, and $\geq 80\% - < 90\%$, etc.

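### The SAP's formula for actual cumulative dose assumes two equal doses every day, which conflicts with its own half-day rule and leaves unequal AM/PM regimens undefined

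*SAP*

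**What the plan says.** SAP 4.6.1.1 defines RDI as 100% × d/D, where "d is the actual cumulative dose delivered up to the actual last day of dosing". It then gives the calculation of d: "The actual cumulative dose will be calculated by summing", over each period on the exposure form, the days on that record times Dose, divided by 0.5. The 0.5 is the half-day dosing interval of the bid schedule that the SAP takes as the intended dose. Percentage compliance in the same section also has the actual cumulative dose as its numerator.

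A few paragraphs earlier, the definition of a dose interruption includes "any half day where planned frequency is bid but actual frequency is daily". Once-daily days are therefore foreseen, and are deducted from actual exposure.

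Protocol Table 7 gives AM and PM doses separately for the first reduction and, under "Second selumetinib dose (mg) reduction", for the second. Table J15 does the same for participants on strong or moderate CYP2C19 or CYP3A4 inhibitors. Many of these pairs are unequal, and the worked example in protocol 6.6 uses one (35 mg AM, 30 mg PM).

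**The concern.** Dividing by a fixed 0.5 is correct only when a record holds one per-administration dose, taken twice every day in equal amounts. Two situations that the documents themselves foresee break that condition: days taken once daily, and regimens with different AM and PM doses. In the first, one section deducts half a day of exposure and then credits a full day of dose. In the second, the formula does not say which number Dose is.

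RDI and compliance exist to show how much drug was delivered to participants who did not stay on the full schedule, so an incorrect d weakens the tables where they are most needed. Compliance is also reported in bands with limits at 80%, 90%, 95% and 100% (SAP 4.6.1.2), so even a modest error can change a participant's band.

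**Working it through.** The documents give no worked cumulative dose, so there is no figure to reproduce.

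**Check on starting doses.** With one per-administration dose per record, the formula is exact for all five starting regimens. At 50 mg bid for 28 days: 28 × 50 / 0.5 = 2800 mg; delivered 28 × (50 + 50) = 2800 mg.

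**Once-daily days.** Take 50 mg bid for 21 days, then 50 mg once daily for 7 days.
- Delivered: 21 × 100 + 7 × 50 = 2100 + 350 = 2450 mg; RDI = 2450 / 2800 = 87.5%.
- SAP formula: 21 × 50 / 0.5 + 7 × 50 / 0.5 = 2100 + 700 = 2800 mg; RDI = 100%.

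This needs only that the dose taken at each administration is what is entered.

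**Unequal AM/PM regimens.** Each table has 5 body-surface-area (BSA) bands and 2 adjustment levels, so 20 cells in all. Unequal cells: Table 7 first reduction 2 of 5, second reduction 4 of 5; Table J15 upper level (20 mg/m²) 2 of 5, lower level (15 mg/m²) 3 of 5. Total 2 + 4 + 2 + 3 = 11.

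For 28 days, delivered dose = 28 × (AM + PM). If one record carries the AM dose, the formula gives 28 × AM × 2, a relative error of 2·AM/(AM + PM) − 1. If it carries the PM dose, the error has the same size with a negative sign.

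| AM/PM (mg) | Cells | Delivered (mg) | Formula, AM entered | Formula, PM entered | Error |
|---|---|---|---|---|---|
| 35/30 | 2 | 1820 | 1960 | 1680 | ±7.7% |
| 30/25 | 2 | 1540 | 1680 | 1400 | ±9.1% |
| 25/20 | 4 | 1260 | 1400 | 1120 | ±11.1% |
| 20/10 | 1 | 840 | 1120 | 560 | ±33.3% |
| 25/10 | 2 | 980 | 1400 | 560 | ±42.9% |

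Thus 8 of the 11 cells err by at most 11.1%. The three larger errors are all at BSA below 1.5 m² and at the lower level of their table. At BSA ≥ 1.90 m² every pair is equal and there is no error.

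In RDI terms, for the days on that regimen and against the starting dose:
- 25/10 at BSA 1.3–1.49 (Table 7, second reduction; start 35/35, 1960 mg): true 980/1960 = 50.0%; formula 71.4% (AM entered) or 28.6% (PM entered).
- 25/10 at BSA 1.10–1.29 (Table J15, lower level; start 30/30, 1680 mg): true 980/1680 = 58.3%; formula 83.3% or 33.3%.

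For compliance, take a fully compliant participant on 35/30 with a correctly computed denominator. The formula gives 1680/1820 = 92.3% or 1960/1820 = 107.7%.

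**Other ways of entering Dose.**
- AM and PM as separate records: 28 × AM × 2 + 28 × PM × 2, twice the delivered dose. This reaches starting doses too: 30/30 gives 3360 mg instead of 1680 mg.
- Total daily dose: 28 × (AM + PM) × 2, again twice the delivered dose.
- Mean of AM and PM: 28 × (AM + PM)/2 × 2, which is correct for unequal regimens. The SAP states no such convention.

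**The case against.** The strongest objection is that the exposure form is not in the documents. Whether an unequal regimen comes out wrong, and in which direction, depends on how Dose is entered, and one convention (the mean) gives no error. That stands as a limit on the size. It does not rescue the formula, because the SAP does not state that convention and every other layout considered gives a wrong total. The reference in SAP 4.6.1.2 to "start and end date of interruption/reduction and dose per administration" points towards a per-administration entry, under which the 11 cells fail.

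A second objection is that these are descriptive summaries, and that SAP 4.6.1.2 separately reports actual exposure, the numbers of interruptions and reductions, and the details of each. That also stands. A reader might infer that dose loss would go unseen; the separate reporting means it would not, although RDI and compliance would disagree with it.

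Third, a reader might take 11 of 20 to mean that over half of dose-adjusted participants are affected. The count is of table cells, and the documents give no distribution of participants across them. The error also applies only to days on that regimen, so RDI over a whole period is diluted.

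Fourth, it is tempting to say that the error falls only on dose-adjusted or partly dosed participants. That holds on the single-record reading. If AM and PM are routinely entered separately, or total daily dose is entered, starting doses are doubled as well, and RDI near 200% for participants on full dose would be noticed as a programming fault.

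**Conclusion.** The formula should be corrected. The firmest part is the conflict within SAP 4.6.1.1: a once-daily day counts as half a day of exposure but a full day of dose. In the example, RDI is overstated by 12.5 percentage points. For unequal AM/PM regimens, Dose is not validly defined in 11 of 20 adjusted cells. On a single per-administration record the error, in either direction, is 7.7% to 11.1% in 8 cells, 33.3% in 1 and 42.9% in 2, for the days on that regimen. It is zero only under an unstated mean-dose convention, and +100% for every regimen entered as separate AM and PM records or as a total daily dose.

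These sizes assume that the form records doses actually taken; its layout is unknown. The effect is confined to the RDI and compliance summaries. A reader might infer a consequence for the efficacy results, but no endpoint, test or analysis set uses these quantities. The point concerns the exposure derivation only and takes no position on the doses in either table.

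**What to change.** Replace the formula in SAP 4.6.1.1 with: actual cumulative dose = sum over exposure records of days × dose per administration × administrations actually taken per day. Unequal AM and PM doses are then added, not doubled, and a once-daily day contributes one dose. Use this quantity as the numerator of both RDI and compliance. State how an AM/PM-split regimen is entered on the exposure form, and that a split recorded as two once-daily records is not a half-day interruption.

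The cost is one SAP formula and the matching program. The interruption rule already relies on dates, dose and actual frequency, and SAP 4.6.1.2 already refers to dose per administration, so new data collection should not be needed. That should be confirmed against the form.
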